7.1.6 Discontinuation of study treatment

Patients may voluntarily discontinue from the study treatment for any reason at any time. If a patient decides to discontinue from the study treatment, the investigator should make a reasonable effort (e.g. telephone, e-mail, letter) to understand the primary reason for this decision and record this information in the patient’s chart and on the appropriate eCRF pages. They may be considered withdrawn if they state an intention to withdraw, fail to return for visits, or become lost to follow-up for any other reason.

The investigator should discontinue study treatment for a given patient if, he/she believes that continuation would be detrimental to the patient’s well-being. Patients who discontinue study treatment should undergo an end of study visit.

For patients who discontinue treatment for reasons other than death, lost to follow-up, or withdrawal of consent, the patient should enter the survival follow-up phase. Survival visit assessments (survival, antineoplastic therapies, stem cell transplant and progression) should be performed every 12 weeks until documented death, lost to follow-up, or withdrawal of consent.

Patients who discontinue the study treatment for an adverse event suspected to be related to study drug or an abnormal laboratory value suspected to be related to study drug must be followed as described in [Section 8](#).

Patients may also be discontinued from the study treatment if any of the following occurs:

- discovery of patient ineligibility
- errors in treatment compliance [study treatment, other prescribed or non-prescribed medications]
- missed/unscheduled/off schedule/incomplete/incorrect assessments
- major protocol deviation
- pregnancy during treatment phase
- use of prohibited treatment refer to [Appendix 1](#).
- any other protocol deviation that results in a significant risk to the patient's safety

In addition to the general discontinuation criteria, the following study specific criteria will also require discontinuation of study treatment:

In the event of treatment failure the patient must be discontinued from the study treatment. The following events will constitute 'treatment failure', and are based on the ELN criteria ([Bacarrani 2013](#)) defining failure of a second line treatment:

- No CHR or > 95% Ph+ metaphases at three months after randomization or thereafter
- BCR-ABL ratio > 10% IS and/or > 65% Ph+ metaphases at six months after randomization or thereafter

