- BCR-ABL ratio > 10% IS and/or > 35% Ph+ metaphases at 12 months after randomization or thereafter
- Loss of CHR, CCyR or PCyR at any time after randomization
- Detection of new BCR-ABL mutations at any time after randomization
- Confirmed loss of MMR in 2 consecutive tests, of which one must have a BCR-ABL ratio $\geq 1\%$ IS 6 months after randomization
- New clonal chromosome abnormalities in Ph+ cells: CCA/Ph+: at any time after randomization

In the event of disease progression the patient must be discontinued from the study treatment. The following events are considered disease progression.

1. CML-related death (any death during treatment or follow-up if the principal cause of death is marked as "study indication" in the eCRF by the investigator, or if the death occurred subsequent to documented progression to AP/BC and the cause of death is reported as "unknown" or not reported by the investigator)
2. Accelerated phase (AP) as defined by any of the following:
 - $\geq 15\%$ blasts in the peripheral blood or bone marrow aspirate, but $< 30\%$ blasts in both the peripheral blood and bone marrow aspirate
 - $\geq 30\%$ blasts plus promyelocytes in peripheral blood or bone marrow aspirate
 - $\geq 20\%$ basophils in the peripheral blood
 - Thrombocytopenia ($< 100 \times 10^9/L$) that is unrelated to therapy

3. Blast crisis (BC) as defined by any of the following:
- $\geq 30\%$ blasts in peripheral blood or bone marrow aspirate
 - Appearance of extramedullary involvement other than hepatosplenomegaly proven by biopsy (i.e., chloroma).

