7.2 Assessment types

7.2.1 Efficacy assessments

7.2.1.1 Molecular response

Molecular response (MR) will be assessed in all patients randomized to each treatment arm.

Levels of BCR-ABL transcripts will be determined by real-time quantitative PCR (RQ-PCR) testing of peripheral blood and analyzed at a central testing laboratory. Log reduction in BCR-ABL transcripts levels from the standardized baseline value, or the percent ratio of BCR-ABL transcripts versus control gene (ABL) transcripts converted to a reference standard, international scale ([Hughes and Branford 2006](#)), will be calculated for each sample.

Major molecular response and related variables are defined as the following:

- Rate of Major Molecular Response (MMR) where MMR is defined as a ≥ 3.0 log reduction in BCR-ABL transcripts compared to the standardized baseline equivalent to $\leq 0.1\%$ BCR-ABL/ABL % by international scale as measured by RQ-PCR, confirmed by duplicate analysis of the same sample
- Time to MMR defined as the time from the date of randomization to the date of the first documented MMR,
- Duration of MMR defined as the time from the date of first documented MMR to the earliest date of loss of MMR, progression to AP or BC, or CML-related death.

Loss of MMR is defined as confirmed loss of a greater than or equal to 3.0 log reduction in BCR-ABL transcript levels compared to the standardized baseline value, or confirmed loss of a less than or equal to 0.1% BCR-ABL/ABL by international scale in association with a ≥ 5 -fold rise in BCR-ABL from the lowest value achieved on study treatment confirmed by a duplicate analysis of the same sample. This result has to be confirmed by a subsequent sample within 4-6 weeks unless it is associated with confirmed loss of CHR or loss of CCyR or progression to AP/BC or CML-related death.

Mutational analysis will be performed at a Novartis designated laboratory by Sanger sequencing at baseline and at end of treatment. If the result at baseline is positive for a mutation, analysis will be performed every 12 weeks.

The blood samples will be taken as described in [Table 7-1](#) and [Table 7-2](#).

Table 7-2 Blood samples (efficacy primary endpoint)

[figure not shown]
Sample Type	Volume	Visit	Time point
Blood for BCR-ABL quantification by RQ-PCR	20 mL	Screening/Baseline	Pre-dose
	20 mL	Week 4	Pre-dose
	20 mL	Week 8	Pre-dose
	20 mL	Week 12	Pre-dose
	20 mL	Week 16	Pre-dose
	20 mL	Week 24	Pre-dose
	20 mL	Week 36	Pre-dose

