10.5.2 Other secondary efficacy objectives

Unless otherwise stated the FAS will be used for the analysis of all other secondary efficacy endpoints. The exceptions are using the Molecular Responder Set for duration of MMR and time to MMR, the CCyR Analysis Set for CCyR rates, and the Cytogenetic Responder Set for duration of CCyR and time to CCyR.

No statistical testing of non-key secondary efficacy endpoints will be performed, however a nominal p-value will be presented for exploratory purposes.

Molecular Response

MMR rates at scheduled time points (except 24 and 96 weeks which have been specified as primary and key secondary endpoints) will be evaluated in a similar fashion to the primary analysis of MMR rate at 24 weeks. Patients discontinuing the randomized treatment prior to a specific time point due to any reason will be considered as non-responders for that time point.

MMR rates by scheduled time points are defined as the proportion of patients who achieve MMR at or before the specified visit, i.e. if a patient achieves an MMR but then loses it before or at the visit, he/she will still be classed as achieving MMR by that time point.

For each endpoint the rate and the associated 95% confidence interval based on the Pearson-Clopper method will be presented by treatment group. Confidence intervals for the differences in any response rates between treatment groups will be provided using the Wald method.

Statistical testing will be performed via CMH chi-square tests stratified by the randomization strata. The Mantel-Haenszel estimate of the common risk difference and the corresponding 95% confidence interval will also be provided.

Duration of MMR is defined in [Section 7.2.1.1](#) as the time between the date of the first documented MMR and the earliest date of loss of MMR, progression to AP/BC, or CML-related death for patients in the Molecular Responder Set. The time will be censored at the last molecular assessment (PCR) date on treatment for patients who have not experienced any of the above events.

Duration of MMR will be analyzed by K-M method and presented by K-M plots. The estimated rates of patients who are still responding at various time points will also be provided using K-M method.

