Duration of CCyR is defined as the time between date of first documented CCyR and the earliest date of loss of CCyR, progression to AP/BC, or CML-related death for patients in the Cytogenetic Responder Set. The time will be censored at the last cytogenetic assessment date on treatment for patients for whom none of the above events is reported or last PCR evaluation on treatment indicating MMR.

Duration of CCyR response will be analyzed by K-M method and presented by K-M plots. The estimated rates of patients who are still responding at various time points will also be provided using K-M method.

Treatment failure, disease progression and survival

Time to treatment failure (TTF) is defined as the time from date of randomization to an event of treatment failure. The following events will constitute ‘treatment failure’, and are based on the ELN criteria ([Bacarrani 2013](#)) defining failure of a second line treatment adapted to include discontinuation of randomized treatment as an event:

- No CHR or > 95% Ph+ metaphases at three months after randomization or thereafter
- BCR-ABL ratio > 10% IS and/or > 65% Ph+ metaphases at six months after randomization or thereafter
- BCR-ABL ratio > 10% IS and/or > 35% Ph+ metaphases at 12 months after randomization or thereafter
- Loss of CHR, CCyR or PCyR at any time after randomization
- Detection of new BCR-ABL mutations at any time after randomization
- Confirmed loss of MMR in 2 consecutive tests, of which one must have a BCR-ABL ratio $\geq 1\%$ IS 6 months after randomization
- New clonal chromosome abnormalities in Ph+ cells: CCA/Ph+: at any time after randomization
- Discontinuation from randomized treatment for any reason

For patients who have not reach treatment failure, their TTFs will be censored at the time of last study assessment (PCR, cytogenetic, hematologic or extramedullary).

Progression-Free-Survival (PFS) is defined as the time from the date of randomization to the earliest occurrence of documented disease progression to AP/BC or the date of death from any cause (including progressions and deaths observed during the survival follow-up period).

The time will be censored at the date of last study assessment (PCR, cytogenetic, hematologic or extramedullary) or last post-treatment follow-up for patients without event.

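### Duration of MMR and of CCyR set no on-treatment limit on progression or CML death, yet censor event-free patients at their last on-treatment assessment

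*Combined protocol and SAP*

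**What the plan says.** The relevant text is in the Amendment 1 protocol.

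- **Events, MMR.** Section 10.5.2 runs duration of MMR from first documented MMR to "the earliest date of loss of MMR, progression to AP/BC, or CML-related death for patients in the Molecular Responder Set". Section 7.2.1.1 has the same end point: "to the earliest date of loss of MMR, progression to AP or BC, or CML-related death".
- **Events, CCyR.** Section 10.5.2 uses "the earliest date of loss of CCyR, progression to AP/BC, or CML-related death for patients in the Cytogenetic Responder Set".
- **Reach of the events.** Section 7.1.6 defines "CML-related death (any death during treatment or follow-up if the principal cause of death is marked as" the study indication. It also counts a death of unknown or unreported cause after documented AP/BC. The AP/BC definitions in the same list carry no time limit.
- **Collection after stopping drug.** Section 7.1.6: "Survival visit assessments (survival, antineoplastic therapies, stem cell transplant and progression) should be performed every 12 weeks until documented death", loss to follow-up or withdrawal of consent.
- **Censoring, MMR.** "The time will be censored at the last molecular assessment (PCR) date on treatment for patients who have not experienced any" of the listed events.
- **Censoring, CCyR.** "The time will be censored at the last cytogenetic assessment date on treatment for patients for whom none of the above events is reported"; the alternative date is the last on-treatment PCR showing MMR.
- **Use.** Section 10.5.2 analyses both durations by Kaplan-Meier, with plots and estimated proportions still in response at various times.

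**The concern.** Kaplan-Meier needs the decision to keep a patient at risk to be independent of what happens to him later. Here it is not. Take two responders who stop study drug at month 6, both in MMR. One progresses to AP at month 30 in survival follow-up. He counts as at risk and in response for 24 further months without a scheduled PCR, and then as an event. The other stays well and leaves the risk set at month 6. Only the later event separates them.

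Late risk sets then hold patients still on drug plus those off-drug patients who are going to have an event. The effect grows with the number of responders who stop drug in response, so it may differ between arms. Durability of response is a listed secondary endpoint and will be read by arm from these curves.

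**Working it through.** **The plan's own figures.** The plan states no figure for either duration. The sample size of 222 concerns the primary endpoint and plays no part here.

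**Windows side by side (Section 10.5.2, with 7.1.6)**

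| Endpoint | Events counted | Event-free patients censored at |
|---|---|---|
| Duration of MMR | CML death: treatment or follow-up (explicit). AP/BC: no limit stated | last on-treatment PCR |
| Duration of CCyR | same | last on-treatment cytogenetic assessment, or PCR showing MMR |
| PFS | survival follow-up included (explicit) | last study assessment or last post-treatment follow-up |

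PFS gives both groups follow-up time. The two durations do not.

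**Hand example (assumed counts).** Of 50 responders, 20 stop drug event-free at week 24. Two of those 20 progress at week 72. Everyone else is event-free to week 96. The week-96 estimates are:

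- As written: 18 are censored at week 24, so 50 − 18 = 32 are at risk at week 72, and 1 − 2/32 = 93.8%.
- Full follow-up for all: 1 − 2/50 = 96.0%.
- On-treatment events only: no event, 100%.

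Against full follow-up, the written rule has the same events and smaller risk sets, so it cannot be higher. Against on-treatment only, it adds late events while slightly enlarging earlier risk sets. The net was lower in every setting run.

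**Simulation inputs.** The documents give none of the event rates, so these are assumptions.

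- Responders: 53% of 148 = 78 (asciminib) and 30% of 74 = 22 (bosutinib), using the 96-week rates in Section 10.9.
- Loss of MMR: 5% and 8% a year. Stopping drug in MMR: 10% and 25% a year.
- Follow-up after first MMR: uniform, 1 to 3.5 years. All times exponential.
- Off-treatment AP/BC or CML death: varied. The only background figure is the 5-year PFS and OS of 80 to 95% on TKIs in Section 1.1. This gives 1 − 0.95^(1/5) = 1.0% and 1 − 0.80^(1/5) = 4.4% a year. That population is general, so these are reference points only.

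**Fall in the 2-year rate, written rule against on-treatment only (points)**

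| Off-treatment rate per year | Asciminib | Bosutinib |
|---|---|---|
| 1% | 0.2 | 0.5 |
| 2% | 0.4 | 1.0 |
| 4.4% | 0.8 | 2.1 |
| 10% | 90.5 − 88.8 = 1.7 | 85.2 − 80.8 = 4.4 |

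Repeat runs agree to within a few tenths of a point. The standard error of the 2-year rate is about 3.8 points (asciminib) and 9.5 points (bosutinib). Up to 4.4% a year the shift is therefore at most about 0.2 standard errors, from fewer than one off-treatment event per arm.

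**Both consistent rules.** A second grid used, per 48 weeks, on-treatment loss of 5 to 10%, stopping in response of 10 to 25%, and off-treatment events of 2 to 10%. At week 96 the written rule was 0.4 to 5.5 points below on-treatment only and 0.9 to 4.8 points below full follow-up.

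**The case against.** **AP/BC progression may be meant on treatment only.** The follow-up wording in Section 7.1.6 attaches to CML-related death alone. Where Section 10.5.2 wants follow-up progressions, under PFS, it says so. A reader might infer that the plan expressly counts off-treatment AP/BC progression, and it does not. For AP/BC the open window comes from silence, together with collection of progression off treatment. This stands as a limit on the claim. The mismatch is explicit for CML death and unresolved for AP/BC.

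**The text may be superseded.** The Amendment 3 protocol is supplied only up to Section 7.1.2, so its Section 10.5.2 cannot be read, and no separate SAP text on this rule is available. The change logs for Amendments 2 and 3 list edits to Section 10.5.2 (descriptive statistics, p-values, the BCR-ABL1 threshold). They also list a rephrased loss-of-MMR definition and clarified responder sets, but no change to this censoring rule. Whether it persists cannot be confirmed.

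**The window is bounded.** The end-of-treatment analysis cuts off 30 days after the last dose, and the 5-year update in Section 10.7 covers only PFS and OS. The Amendment 3 rationale also keeps post-switch efficacy data out of the secondary endpoints. This reduces the number of off-treatment events but does not remove them. Treatment runs at least 96 weeks beyond the last patient's first dose, so an early enrollee who stops can have long off-treatment follow-up before the cut-off.

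**The rates still responding need not be too low.** This stands. Tables 7-1 and 7-2 schedule no PCR after end of treatment, so losses of response after stopping go unseen, and that could push the curve up. The simulation assumes that stopping drug leaves the loss rate unchanged.

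**The endpoints are minor.** This also stands. They are non-key and restricted to responders. Section 10.5.2 specifies log-rank tests and hazard ratios only for TTF, PFS and OS.

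**Conclusion.** The point holds in the supplied Section 10.5.2, with minor weight. Events and censoring use different windows, explicitly for CML-related death and by absence of a limit for AP/BC progression. Risk-set membership after stopping drug therefore depends on a later event, and the Kaplan-Meier rate comes out below that from either consistent rule.

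On the assumed inputs, the 2-year shift against on-treatment only is under 1 point (asciminib) and up to about 2 points (bosutinib) at off-treatment rates of about 1 to 4% a year. At 10% a year it is about 2 and 4 points.

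A reader might go further and conclude that the plan understates true response duration, or that the comparison of the arms is seriously distorted. The documents support neither. Loss of response is not assessed on schedule after end of treatment, so the direction against the truth cannot be fixed. No document gives the off-treatment event rate in patients who stop while in response. The primary and key secondary results do not depend on this rule.

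**What to change.** Give events and censoring the same window in both definitions. Suggested wording for the main analysis: loss of response, progression to AP/BC and CML-related death count only while the patient is on randomised treatment, up to and including the end-of-treatment assessment. All other patients are censored at their last assessment in that same window: PCR for MMR, and cytogenetics or a PCR confirming MMR for CCyR. Adding a 30-day tail to the events alone would leave a smaller version of the same mismatch.

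Optionally, add a sensitivity analysis on the PFS pattern, in which follow-up events count and event-free patients are censored at last post-treatment follow-up. First check the current Section 10.5.2 and the SAP for the rule in force.

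The cost is one sentence per endpoint and no new data. A few late AP/BC events and deaths leave response duration; they still count in PFS, and the deaths in OS.

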4.3 Definition of end of study

The end of the study will occur 5 years from the date when the last patient enrolled into the study received the first dose of the randomized treatment.

The primary analysis (cut-off date) is defined as the date when all randomized patients have been on treatment for 24 weeks ([Section 10.4](#)) or discontinued early. Subsequent to this analysis, the primary clinical study report (CSR) will be developed. Following the cut-off date for the primary CSR, the study will remain open. Patients who are ongoing at the time of the primary analysis will continue to receive the assigned study treatments (ABL001 or bosutinib) for up to 96 weeks after the last patient received the first study dose i.e., patients who are benefiting from their study treatment can continue to receive the treatment for up to a period of approximately 2 years following the completion of study enrollment. The end of study treatment analysis will be conducted with a cut-off date 30 days after last patient receives the last study dose to ensure all available treatment data from all patients in the study is analyzed and summarized in a CSR.

After the end of the study treatment period the assigned study treatment will be made available to patients who in the opinion of the Investigator are still deriving clinical benefit. This may be outside of this study through alternative options including, but not limited to, an expanded access/compassionate use /managed access program or access to commercial supplies in applicable countries.

Patients will be followed up for survival and progression for up to 5 years from the date the last patient received the first study dose. Information on subsequent treatments will also be collected. An updated analysis of OS and PFS will be performed at the end of the follow-up period.

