6.1.5 Treatment duration

There is no fixed duration of treatment planned per patient. All patients will be given the opportunity to receive study treatment until the date that corresponds to 96 weeks after the last patient receives the first study dose. Patients may be discontinued from treatment with the study drug at any time due to unacceptable toxicity, disease progression and/or at the discretion of the investigator or the patient.

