9.4 Database management and quality control

For studies using eCRFs, Novartis personnel (or designated CRO) will review the data entered by investigational staff for completeness and accuracy. Electronic data queries stating the nature of the problem and requesting clarification will be created for discrepancies and missing values and sent to the investigational site via the EDC system. Designated investigator site staff are required to respond promptly to queries and to make any necessary changes to the data.

Concomitant treatments and prior medications entered into the database will be coded using the WHO Drug Reference List, which employs the Anatomical Therapeutic Chemical classification system. Medical history/current medical conditions and adverse events will be coded using the Medical dictionary for regulatory activities (MedDRA) terminology.

Samples and/or data will be processed centrally and the results will be sent electronically to Novartis (or a designated CRO).

Randomization codes and data about all study treatments dispensed to the patient and all IRT assigned dosage changes will be tracked using the Novartis Interactive Response Technology.

For EDC studies, after database lock, the investigator will receive a CD-ROM or paper copies of the patient data for archiving at the investigational site.

10 Statistical methods and data analysis

The data will be analyzed by Novartis and/or designated CRO. It is planned that the data from participating centers in this protocol will be combined, so that an adequate number of patients will be available for analysis.

Study data will be summarized with respect to demographic and baseline characteristics, efficacy observations and measurements, safety observations and measurements, and all relevant PK and PD measurements.

The cut-off date for the primary analysis is defined as the date when all patients have been on study for 24 weeks or early discontinued. The cut-off date for the final treatment phase analysis is defined as 30 days after last patient last study drug to ensure that all available treatment phase data from all patients up to the last dose of study drug taken in this study, will be analyzed and summarized in a final treatment phase CSR. Patients will be further followed up for survival and progression for up to 5 years from the date the last patient received the first study dose. An update analysis of OS and PFS will be performed at the end of the follow-up period.

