Study treatment	Includes any drug or combination of drugs in any study arm administered to the patient (subject) as part of the required study procedures, including placebo and active drug run-ins. In specific examples, it is important to judge investigational treatment component relationship relative to a study treatment combination; study treatment in this case refers to the investigational and non-investigational treatments in combination.
Study treatment discontinuation	Point/time when patient permanently stops taking study treatment for any reason
Treatment group	A treatment group defines the dose and regimen or the combination, and may consist of 1 or more cohorts. Cohorts are not expanded, new cohorts are enrolled.
Variable	Identifier used in the data analysis; derived directly or indirectly from data collected using specified assessments at specified time points
Withdrawal of study consent	Withdrawal of consent from the study occurs only when a subject does not want to participate in the study any longer, and does not allow any further collection of personal data

Protocol summary:

Title	A phase 3, multi-center, open-label, randomized study of oral ABL001 (asciminib) versus bosutinib in patients with Chronic Myelogenous Leukemia in chronic phase (CML-CP), previously treated with 2 or more tyrosine kinase inhibitors
Brief title	Study of efficacy of CML-CP patients treated with asciminib versus bosutinib, previously treated with 2 or more TKIs
Sponsor and Clinical Phase	Novartis Phase 3
Investigation type	Drug
Study type	Interventional

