4.3 Definition of end of study

The patients are treated in the study up to end of study treatment period defined as up to 96 weeks after the last patient receives the first dose or up to 48 weeks after the last patient has switched to asciminib treatment whichever is longer unless patients have discontinued treatment earlier. The end of the study, concluding the survival follow-up, will occur 5 years from the date when the last patient enrolled into the study receives the first dose of the randomized treatment.

The primary analysis (cut-off date) is defined as the date when all randomized patients have been on study treatment for 24 weeks ([Section 10.4](#)) or discontinued earlier. Subsequent to this

analysis, the primary clinical study report (CSR) will be developed. Following the cut-off date for the primary CSR, the study will remain open. Patients who are ongoing at the time of the primary analysis will continue to receive the assigned study treatments (asciminib or bosutinib) during the study treatment period as defined above. The end of study treatment analysis will be conducted with a cut-off date 30 days after the end of study treatment period to ensure all available treatment data from all patients in the study is analyzed and summarized in a CSR.

After the end of the study treatment period the assigned study treatment will be made available to patients who in the opinion of the Investigators are still deriving clinical benefit. This may be outside of this study through alternative options including, but not limited to, an expanded access/compassionate use /managed access program or access to commercial supplies in applicable countries.

Patients will be followed for survival and progression for up to 5 years from the date the last randomized patient receives the first study dose (irrespective of treatment switch for patients failing bosutinib). Information on subsequent treatments will also be collected. An updated analysis of OS and PFS will be performed at the end of the follow-up period in the final study CSR.

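### Time to treatment failure has no exception for the planned end of study treatment, so a literal coding at the end-of-treatment analysis turns patients who complete without failing into failures

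*Combined protocol and SAP*

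**What the plan says.** Section 10.5.2 of the Amendment 1 protocol builds TTF on the ELN failure criteria, "adapted to include discontinuation of randomized treatment as an event". The last bullet of the event list is "Discontinuation from randomized treatment for any reason". The censoring rule follows: "For patients who have not reach treatment failure, their TTFs will be censored at the time of last study assessment". TTF is analysed by Kaplan-Meier, a stratified log-rank test and a stratified Cox model.

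The glossary, in both protocol versions, defines study treatment discontinuation as "Point/time when patient permanently stops taking study treatment for any reason".

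Treatment ends by design. In Amendment 1, Section 6.1.5, patients may be treated "until the date that corresponds to 96 weeks after the last patient receives the first study dose". Amendment 3, Section 4.3, says: "The patients are treated in the study up to end of study treatment period defined as up to 96 weeks after the last patient". The clock there starts at that patient's first dose, and the period is extended if a point 48 weeks beyond the final bosutinib-to-asciminib switch falls later.

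The analysis follows that end. Amendment 1, Section 4.3: "The end of study treatment analysis will be conducted with a cut-off date 30 days after last patient receives the last study dose". The introduction to Section 10 agrees: "The cut-off date for the final treatment phase analysis is defined as 30 days after last patient last study drug". Amendment 3, Section 4.3, sets the cut-off 30 days after the end of the study treatment period.

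**The concern.** At the end-of-treatment cut-off, every patient has stopped study treatment within the study. Some stopped because they failed, did not tolerate the drug or withdrew. The rest stopped only because the treatment period closed. The event bullet does not separate the two groups, and the glossary is equally broad. A programmer who follows the text would give the second group an event on the day the period closed.

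Those stops say nothing about the drugs. They occur on a calendar date common to both arms, and there are more of them in whichever arm keeps more patients on treatment. TTF would then understate a difference in durability between the arms and report medians that partly reflect the trial's closing date.

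**Working it through.** **Is there a figure to reproduce?** The documents give no event count, failure rate or hazard ratio for TTF. The arm sizes, 148 and 74, come from Section 10.8. That total of 222 reproduces (pooled-variance formula without continuity correction, 74 controls, power 90.3%), but nothing below depends on it.

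**Who is affected, and when.** The planned end is at least 96 weeks after the last patient's first dose, so no patient reaches it before about week 96. Under Amendment 3 a switch is allowed until 96 weeks after the last randomization (Section 4.1.1), and treatment may run 48 weeks beyond the last switch. The latest end is therefore about 96 + 48 = 144 weeks after the last patient starts. Amendment 1 schedules visits to week 168, which suggests accrual of about 168 − 96 = 72 weeks. That is inferred, not stated.

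**Assumptions for size.** Failure times are exponential with rate λ, and the planned end is uniform between *a* and *b* weeks from a patient's start. The medians and the failure proportions at week 96 are illustrative.

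**Share still on drug at the planned end:** p = (e^(−λa) − e^(−λb)) / (λ(b − a)).

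- Medians 40 (bosutinib) and 100 weeks (asciminib), a = 96, b = 190.
- Asciminib: λ = ln 2/100 = 0.00693; p = (0.514 − 0.268)/0.652 = 0.38, or 56 of 148.
- Bosutinib: λ = ln 2/40 = 0.01733; p = (0.189 − 0.037)/1.629 = 0.09, or 7 of 74.
- Artificial failures: 63 of 222, or 28%.

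With a = 96, b = 168 and failure by week 96 of 30% v 60%, 40% v 70% or 50% v 80% (asciminib v bosutinib), the share of all patients is 51%, 40% or 30%.

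**Kaplan-Meier.** With the planned end censored, S(t) = e^(−λt). With it counted as an event, S(t) is multiplied by (b − t)/(b − a) for t between a and b. Before week 96 the two curves are identical. Taking 40% v 70% failed by week 96 and an end at 96 to 168 weeks:

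- Week 144, asciminib: 0.6^1.5 = 0.46 censored; 0.46 × 24/72 = 0.15 as an event.
- Week 144, bosutinib: 0.3^1.5 = 0.16 censored; 0.16 × 24/72 = 0.05 as an event.
- Asciminib median: ln 2/0.00532 = 130 weeks censored; about 105 weeks as an event, since 0.6^(105/96) × 63/72 = 0.50.

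**Hazard ratio.** After week *a*, the event coding adds the same hazard, 1/(b − t), to both arms, so the ratio at time t is (λ_A + 1/(b − t)) / (λ_B + 1/(b − t)). In the 40 v 100 case at week 143 this is (0.00693 + 0.02128)/(0.01733 + 0.02128) = 0.73, against a true 0.40, and it tends to 1 as t approaches b. The Cox estimate θ averages over time. Its large-sample value solves ∫ [dN_A − (dN_A + dN_B) θY_A/(θY_A + Y_B)] = 0, with Y the expected numbers at risk and N the expected events. Unstratified results:

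| Medians, bosutinib v asciminib (weeks) | Planned end censored | Event, end 96–190 | Event, end 96–168 | Event, end 144–238 |
|---|---|---|---|---|
| 40 v 100 | 0.40 | 0.47 | 0.48 | 0.43 |
| 40 v 150 | 0.27 | 0.36 | 0.37 | 0.31 |
| 52 v 200 | 0.26 | 0.41 | 0.42 | 0.35 |

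Simulated trials of 148 v 74 patients agree to about 0.01 to 0.02. For the three week-96 failure scenarios with an end at 96 to 168 weeks, simulation gives 0.39 to 0.57, 0.43 to 0.55 and 0.43 to 0.51. With equal failure of 40% in both arms the hazard ratio is 1.00 under either coding.

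**The case against.** The best reply is that the authors never meant completers to be events. The plan keeps a censoring rule, and a reading that empties it is unnatural. Elsewhere it distinguishes patients who stopped early from those who reached the end of the period (the Section 10 introduction; Amendment 3, Section 4.3). The bullet speaks of randomized treatment while the glossary defines discontinuation of study treatment, and patients still benefiting may go on receiving the assigned drug, possibly outside the study.

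This makes the benign intent plausible but does not settle the coding. The censoring rule is needed anyway at the 24-week analysis. The early-stop wording used elsewhere is missing from the bullet, which says any reason. Supply outside the study is not clearly continued randomized treatment. No passage says how a planned completer is coded.

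A second reply stands as a limit. The TTF text is from Amendment 1. The Amendment 3 text supplied stops in Section 7.1.2, and no SAP text on TTF was available. The change lists for Amendments 2 and 3 do name Section 10.5.2, but they mention no change to the TTF events.

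A reader might infer more than this supports:

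- **That the censoring rule never applies.** It does apply at the 24-week analysis.
- **That TTF is spoiled throughout.** Kaplan-Meier estimates before week 96 are the same under either coding.
- **That the rule favours asciminib.** The pull is towards 1 and creates no false advantage.

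**Conclusion.** The event rule, as written in the Amendment 1 text, lacks a necessary exception. Followed literally at the end-of-treatment analysis, it codes planned completers as failures. The direction is firm: towards no difference, and confined to time from week 96 on. The size is not firm. It rests on assumed exponential failure, assumed medians or failure proportions, and an assumed spread of planned ends. The shift is smaller if treatment runs to the later limit that Amendment 3 allows.

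The inferential weight is modest. TTF has no formal test in Amendment 1, which gives only a nominal p-value, and the Amendment 2 change list removes that. The primary and key secondary MMR endpoints are untouched. This should be fixed but is not critical, and whether the current Section 10.5.2 or the SAP already covers it should be checked first.

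**What to change.** After "Discontinuation from randomized treatment for any reason" add: *other than reaching the end of the study treatment period (Section 4.3)*. State that such patients, if no other failure criterion has been met, are censored at their last assessment on randomized treatment. Duration of MMR and of CCyR already use on-treatment censoring. Apply the same rule to the exploratory switch-phase TTF in Table 3-1 of Amendment 3, with assessments on asciminib after the switch.

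The cost is one or two sentences in the protocol or SAP and a line in the derivation. No new data are needed, because planned completion can be identified from the known end date of the treatment period together with the recorded dosing dates.
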